4.9.2 Clinical safety experience with related ALVAC-HIV vaccines

4.9.2.1 Summary of safety, reactogenicity, and tolerability from related human experience

The tolerability and safety of ALVAC-HIV (vCP1521) were evaluated initially in 2 phase 1-2 studies in Thailand (87, 88). The most relevant data, however, come from the large RV144 efficacy study performed in Thailand (19, 89), during which more than 8000 participants received the vaccine and ALVAC-HIV (vCP1521) was found to be safe and well tolerated. Vaccine recipients experienced local and/or systemic reactions significantly more frequently than placebo recipients; the frequencies of local reactions such as pain and tenderness were higher than those of systemic reactions such as headache, fatigue, arthralgia and myalgia; fever was rarely reported; ALVAC-HIV (vCP1521) was associated with a higher frequency of local reactions compared to the protein subunit used in the study (AIDSVAX B/E); the frequency of both local and systemic reactions gradually declined with subsequent vaccine administrations; most local and systemic reactogenicity symptoms were mild to moderate, resolving rapidly and spontaneously in the vast majority of cases; and the frequencies of adverse events (AEs) and serious adverse events (SAEs) were not different between vaccine and placebo groups (89). Overall, results with ALVAC-HIV (vCP1521) are consistent with other ALVAC-HIV constructs, supporting the conclusion that the safety, reactogenicity, and tolerability profile of ALVAC-HIV is determined in greater measure by the vector than by the HIV genetic material inserted into it.

De Bruyn et al (90) characterized the tolerability and safety profile of ALVAC-HIV (vCP205) and ALVAC-HIV (vCP1452) (along with other ALVAC vectors) based on data from more than 1,000 clinical trial participants. The authors concluded that:

- 1. ALVAC-HIV vaccines were safe and well tolerated, with a reactogenicity profile comparable to that of existing vaccines licensed for use in adults; and
- 2. Reactogenicity was similar for different ALVAC-HIV constructs, suggesting that reactogenicity is determined in greater measure by the vector than by the additional genetic material inserted into the vector.

Of interest as well was the observation that reactogenicity seemed to differ according to certain demographic variables: Black, non-Hispanic participants reported significantly less reactogenicity than did White, non-Hispanic participants; and males reported less pain than females.

Additional information is available in the ALVAC-HIV (vCP2438) IB.

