4.5.5 Choice of control

The control for ALVAC-HIV (vCP2438) and for Bivalent Subtype C gp120/MF59 is sodium chloride for injection, 0.9%.

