4.9.6.1 Interim summary of blinded safety and tolerability data

Blinded safety data reported as of November 2016 are summarized here. A total of 1198 ALVAC or placebo injections were given to participants in the left deltoid and 703 Bivalent Subtype C gp120/MF59 or placebo injections were given to participants in the right deltoid.

The vaccine regimen is very well tolerated thus far with the vast majority experiencing no or mild local reactogenicity symptoms. Mild pain and/or tenderness was reported by 58% of participants for injections in the left deltoid and by 48% for injections in the right deltoid. Moderate pain and/or tenderness was reported by 18% of participants for injections in the left deltoid and by 11% for injections in the right deltoid. Severe pain and/or tenderness was reported from a left deltoid injection by 1 participant (following the 1st injection) and for a right deltoid injection by 2 participants (following the 3rd or 5th injection).

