5.1 Primary objectives and endpoints

Primary objective 1:

To evaluate the vaccine efficacy (VE) of ALVAC-HIV (vCP2438) + Bivalent Subtype C gp120/MF59 for the prevention of HIV infection in HIV-seronegative South African adults over 24 months from enrollment

Per the 23 January 2020 DSMB finding that monitoring boundaries for nonefficacy have been met, Primary objective 1 has been superseded by Primary objective 3 below.

Primary endpoint 1:

HIV-1 infection diagnosed after enrollment (concurrent with first vaccination) through 24 months after enrollment

The main vaccine efficacy endpoint is diagnosis of HIV-1 infection during the follow-up of the trial. The occurrence of HIV-1 infection will be detected through HIV-1 tests administered at specified timepoints. Participants found to be HIV-1– infected will have additional testing to confirm the diagnosis of HIV-1 infection (Section 10.3). The vaccine-induced immune responses may lead to reactive HIV-1 tests and difficulty in interpretation. Therefore, the study will utilize blinded Endpoint Adjudicator(s) to review all data that support diagnoses of HIV-1 infection.

Primary objective 2:

To evaluate the safety and tolerability of ALVAC-HIV (vCP2438) + Bivalent Subtype C gp120/MF59 in adults in South Africa

Primary endpoints 2:

Number and frequency of local and systemic reactogenicity signs and symptoms (pain, tenderness, maximum severity of pain and/or tenderness, erythema, induration, fever, malaise/fatigue, myalgia, headache, nausea, vomiting, chills, arthralgia) occurring within 3 days after each vaccine/placebo dose

AEs by body system, Medical Dictionary for Regulatory Activities (MedDRA) Preferred Term, severity, and assessed relationship to study products within 30 days after each vaccine/placebo dose

SAEs, AEs of special interest (AESIs), and new chronic medical conditions (defined as a new onset or exacerbation of medical condition requiring 2 or more

visits to a medical provider during a period of at least 30 days) occurring at any time throughout the study

AEs leading to early participant withdrawal or early discontinuation of study product(s) administration throughout the study

Primary objective 3:

To evaluate the effect of ALVAC-HIV (vCP2438) +Bivalent Subtype C gp120/MF59 vaccination on HIV acquisition in HIV-seronegative African adults

Primary endpoint 3:

HIV infections diagnosed following enrollment and throughout all participant follow-up

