6.9.3.1 Reactogenicity

The number and percentage of participants experiencing each type of reactogenicity sign or symptom will be tabulated by severity and treatment group and the percentages displayed graphically by arm. For a given sign or symptom, each participant's reactogenicity will be counted once under the maximum severity for all injection visits. In addition, to the individual types of events, the maximum severity of local pain or tenderness, induration or erythema, and of systemic symptoms will be calculated. Kruskal-Wallis tests will be used to test for differences in severity between arms.

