8.1 Vaccine regimen

The schedule of vaccination is shown in Section 3 and additional information is given below.

Group 1

Treatment 1 (T1): ALVAC-HIV (vCP2438) to be administered as 1 mL IM in LEFT deltoid (unless medically contraindicated) at months 0, 1, 3, 6, 12, and 18

AND

Bivalent Subtype C gp120/MF59 (an admixture of 100 mcg of TV1.C gp120, 100 mcg of 1086.C gp120, and MF59C.1) to be administered as 0.5 mL IM in RIGHT deltoid (unless medically contraindicated) at Months 3, 6, 12, and 18

Group 2

Placebo 2 (P2): Placebo for ALVAC-HIV (Sodium Chloride for Injection, 0.9%) to be administered as 1 mL IM in LEFT deltoid (unless medically contraindicated) at months 0, 1, 3, 6, 12, and 18

AND

Placebo for Bivalent Subtype C gp120/MF59 (Sodium Chloride for Injection, 0.9%) administered as 0.5 mL IM in RIGHT deltoid (unless medically contraindicated) at Months 3, 6, 12, and 18

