12.3 AEs requiring immediate PSRT notification and prompt PSRT AE review

Prior to study participants being unblinded to their treatment assignments, certain events require immediate telephone notification by the site to the HVTN Core safety staff. Telephone numbers and email addresses for contacting HVTN Core safety staff are found on the Protocol home page on the HVTN Members' site (https://members.hvtn.org/protocols/hvtn702/SitePages/Home.aspx). For the events described in this section, the site will also email and fax forms immediately.

The events which require immediate telephone notification by the site to the HVTN Core 24 hour safety phone, include:

• Any SAE described by the study site as related to the study vaccination

HVTN Core then immediately notifies the PSRT via email or phone. The Protocol Chair or Co-chair then decides how to review the event (via email or conference call). The PSRT will convene within 24 hours and decide whether the event necessitates a pause in further injections. If the team cannot convene to review the event within 24 hours, the medical officer or protocol chair will make the final decision.

The events which require immediate telephone notification by the site to the RML or CSS include:

- any Grade 4 objective local or systemic reactogenicity signs/symptom, or
- Grade 4 AE related to study product, or
- any Grade 5 event

The RML or CSS notifies the HVTN 702 PSRT as soon as possible during working hours (South Africa Standard time or US Pacific Time, respectively)— or, if the information was received during off hours, by the morning of the next work day. If a prompt HVTN 702 PSRT AE review cannot be completed within 72 hours of notification (excluding weekends and US federal holidays), the medical officer or protocol chair will make the final determination as to whether the event necessitates a pause in further injections.

Subjective reactogenicity symptoms (injection site pain, tenderness, fatigue/malaise, myalgia, arthralgia, chills, headache, and nausea) do not require immediate telephone notification by the site to HVTN Core. Objective reactogenicity signs include injection site erythema/redness, induration/swelling, vomiting, and fever.

If the trial is placed on safety pause, all enrollment and vaccination with the product related to the event that triggered the pause will be held until further notice.

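### Local reactogenicity is counted once per participant with no split by injection site, so the planned safety output cannot show which product causes a local excess

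*Protocol*

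**What the plan says.** Primary endpoint 2 (Protocol 5.1, carried into SAP 7.1) begins with "Number and frequency of local and systemic reactogenicity signs and symptoms" in the 3 days after each dose.

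Under Protocol 8.1, ALVAC or its placebo goes in the left deltoid at Months 0, 1, 3, 6, 12 and 18. The gp120/MF59 injection is "to be administered as 0.5 mL IM in RIGHT deltoid" at Months 3, 6, 12 and 18, and its placebo goes in the same deltoid. Protocol 4.5.5 states: "The control for ALVAC-HIV (vCP2438) and for Bivalent Subtype C gp120/MF59 is sodium chloride for injection, 0.9"%. Each product therefore has a saline counterpart at its own site.

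Protocol 6.9.3.1 says that, for a given sign or symptom, each participant's "reactogenicity will be counted once under the maximum severity for all injection visits". SAP Section 9 repeats the rule. It applies Kruskal-Wallis tests to severity and Barnard's test to four aggregates, two of which are any reactogenicity and reactogenicity of grade 3 or higher. In the SAP Appendix, the closed-report RE1 shell has columns for Total, A and B. The open-report shell has columns by vaccination with the treatment groups pooled.

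The background does distinguish products. For the related products in RV144, Protocol 4.9.2.1 reports that "ALVAC-HIV (vCP1521) was associated with a higher frequency of local reactions compared to the protein subunit used in the study (AIDSVAX B/E"). HVTN 100, which gave the same products, was summarised by site. Protocol 4.9.6.1 gives mild pain and/or tenderness as reported by "58% of participants for injections in the left deltoid and by 48% for injections in the right deltoid".

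**The concern.** Pain, tenderness, erythema and induration belong to an injection site. From Month 3 there are two sites per visit with a different product in each, yet the plan gives one figure per participant per sign. The documents do not say in words that the maximum runs over both deltoids. It follows from allowing one count per participant and from shells with no site column.

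The rule also takes the maximum over all visits. A moderate left-deltoid reaction at Month 0, when only ALVAC or its saline is given, is enough to absorb a moderate right-deltoid reaction at Month 12. Splitting by vaccination number does not solve this, because from the third vaccination each visit still merges the two products.

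What is at stake is attribution. A local excess in the vaccine group could come from either product or both. The final analysis as planned would not say which, although the trial has about 2,700 participants per group and a same-site saline control for each product.

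**Working it through.** **The plan's own safety figures (Protocol 6.4.2).** The upper limit with no events is 1 - 0.025^(1/2700) = 0.137%, which matches the stated 0.14%. Exact two-sided Fisher power at 2,700 per group is 0.914 for 4% vs 6%, close to the stated 90%. For 2% vs 4% it is 0.990, so the stated 90% is conservative there. This does not affect the point. The group size is ample; the definition of what is counted is the limitation.

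**Inputs from Protocol 4.9.6 and 4.9.6.1 (HVTN 100, blinded).** There were 252 participants, 210 vaccine and 42 placebo. Pain and/or tenderness by participant:
- left: mild 58%, moderate 18%, severe 1 participant
- right: mild 48%, moderate 11%, severe 2 participants

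Injections numbered 1198 left and 703 right. I take the grades as mutually exclusive maxima and 252 as the denominator on both sides. Both are assumptions.

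**Moderate or worse, blinded.** Left: 0.18 + 1/252 = 18.4%. Right: 0.11 + 2/252 = 11.8%.

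**Removing the placebo share.** With 210:42 allocation, vaccinee rate = (blinded rate - p0/6) / (5/6), where p0 is the placebo rate at each site. The documents give no HVTN 100 placebo rate, so p0 is varied over 0%, 5% and 10%.

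| p0 | Left | Right | Pooled maximum: nested / independent / disjoint |
|---|---|---|---|
| 0% | 22.1% | 14.2% | 22.1% / 33.1% / 36.2% |
| 5% | 21.1% | 13.2% | 21.1% / 31.5% / 34.2% |
| 10% | 20.1% | 12.2% | 20.1% / 29.8% / 32.2% |

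"Nested" means every right-side reactor also reacts on the left. The share of right-deltoid moderate-or-worse reactors already counted through the left is about 20-22% if the sites are independent and 100% if nested. The remainder are counted but cannot be attributed.

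**Can the pooled comparison be significant on ALVAC alone?** Set the gp120/MF59 rate equal to saline and keep the left rate. With L the left rate, the independent case is 1 - (1 - L)(1 - p0) for vaccine and 1 - (1 - p0)^2 for placebo.

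| p0 | Vaccine vs placebo, nested | Vaccine vs placebo, independent |
|---|---|---|
| 0% | 22.1% vs 0% | 22.1% vs 0% |
| 5% | 21.1% vs 5% | 25.0% vs 9.8% |
| 10% | 20.1% vs 10% | 28.1% vs 19.0% |

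Power for a two-proportion comparison at 2,700 per group is about 100% in every row. I use that comparison as a stand-in for the planned severity test.

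**What a right-deltoid comparison would add.** Against its own saline, power is about 100% for 14.2% vs 0% and for 13.2% vs 5%, and 71% for 12.2% vs 10%. An excess detectable at 90% power on the right alone is 5% vs 7.15%, or 2.15 points. In the pooled maximum the same excess moves the vaccine rate by (1 - 0.2108) x 2.15 = 1.7 points if the sites are independent, and by 0 if nested.

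**Is ALVAC the more reactogenic injection?** Injections per participant are 1198/252 = 4.75 left and 703/252 = 2.79 right. If injections were independent (an assumption), the moderate-or-worse rate per injection is 1 - (1 - 0.184)^(1/4.75) = 4.2% left and 1 - (1 - 0.118)^(1/2.79) = 4.4% right. The higher left-side participant rate may simply reflect more left-side doses.

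**The case against.** The strongest reply is that primary objective 2 concerns the combined regimen and that this trial schedules gp120/MF59 only together with ALVAC. The overall maximum answers that objective. This stands, and it is why the maximum should be kept. It does not supply the product-level result.

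The masking is also partial. A right-deltoid reaction graded above the left one still shows. Severe pain in HVTN 100 was 1 left and 2 right, so the loss is at equal or lower grades. The shells are marked as drafts and serve DSMB reports, but the counting rule in the Protocol and SAP text is not a draft.

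A reader might infer more than the documents support:
- *That ALVAC is the more reactogenic injection.* The RV144 remark in Protocol 4.9.2.1 compares vCP1521 with AIDSVAX B/E, an alum-adjuvanted protein (Protocol 4.9.3.2). The HVTN 100 per-injection rates are about equal.
- *That the right deltoid isolates gp120/MF59 alone.* Everyone assigned it is also scheduled for ALVAC at the same visit and at Months 0 and 1. Only those still being vaccinated at Month 3 contribute, and related reactions can stop vaccination earlier (Protocol 7.3.3).
- *That product-level pauses are undermined.* Protocol 12.3 says that "vaccination with the product related to the event that triggered the pause will be held", but those pauses follow review of individual events, not RE1 rates. Subjective pain and tenderness are exempt from immediate notification, and vaccinations have ended.
- *That the Barnard aggregates need splitting.* As worded they are not confined to local signs, and systemic symptoms have no deltoid.
- *That the trial cannot report by site.* It does not plan to. Sites are fixed and labelled, and measurements are recorded for all injection-site reactions (Protocol 9.9.2).

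On sex, the remark that "males reported less pain than females" concerns earlier ALVAC constructs, and unstratified tests remain valid under the randomization. Only a minor addition follows.

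**Conclusion.** The point holds as a gap in the analysis of a primary safety endpoint. The once-per-participant maximum hides right-deltoid reactions at or below the left-deltoid grade, and the pooled local comparison can be significant with no gp120/MF59 effect: 20-28% against 0-19% in the cases shown. A right-side excess of 2.15 points, detectable by itself, would shift the pooled rate by 0 to 1.7 points.

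The structural conclusion needs only the counting rule and the two-site schedule. The sizes rest on blinded HVTN 100 pain and tenderness data, exclusive grades, a common denominator of 252, assumed placebo rates of 0-10%, and overlap between sites from none to complete. The conclusion is about attribution between co-administered products. It does not show that either product is the worse tolerated. Because vaccinations and DSMB oversight have ended, it bears on the final reactogenicity analysis.

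**What to change.** In SAP Section 9, with matching wording in Protocol 6.9.3.1 and in the final RE1 tables:

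- Tabulate local signs by treatment group separately for the left-deltoid injection (ALVAC vs its saline) and the right-deltoid injection (gp120/MF59 vs its saline, among those vaccinated from Month 3). Do this by vaccination visit and overall, with the group difference and 95% CI.
- Classify contralateral or same-deltoid injections by the product documented under Protocol 8.4.
- Keep the overall maximum and the Barnard aggregates, labelled as regimen-level summaries.
- State that the right-deltoid contrast is for gp120/MF59 co-administered with ALVAC.
- If pain and tenderness were not captured by site, limit the split to erythema and induration and say so. The case report forms are not in the documents, so this must be checked first.
- As a minor addition, show the table by sex at birth and stratify the local comparison by sex, already a randomization stratum (Protocol 6.7).

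The cost is SAP wording and a few extra tables. No new data are collected.

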4.9.2.2 Summary of pregnancy occurrence and outcomes

In study RV144 a total of 967 (30.6%) vaccine (vCP1521) and 955 (30.1%) placebo recipients reported a pregnancy during the study while 139 vaccine and 116 placebo recipients reported more than one pregnancy. Birth was reported for 1843 infants, 14 of them representing 7 twin pairs. Of these, 277 births (137

vaccine and 140 placebo recipients; 1 twin pair per treatment) occurred within 450 days of study entry. For these infants, birth weight, gestational age, and Apgar scores were similar between the vaccine and placebo groups. Three congenital abnormalities (1 vaccine and 2 placebo recipients) were reported among these 277 births, the vaccine group abnormality being a respiratory distress syndrome with patent *ductus arteriosus*. Abnormal pregnancy outcomes were experienced in 165 out of 3165 (5.2%) vaccine female recipients and 139 out of 3169 (4.4%) placebo female recipients (p = 0.13), and in 17.1% and 14.6% (p = 0.13) of vaccine and placebo pregnancies, respectively (89).

A total of 15 of the 245 female participants became pregnant during the phase 1-2 AVEG studies. Twelve participants received ALVAC-HIV (vCP205) and 3 received placebo. Of these 15 participants aged 19 to 37 years, 9 participants had live births, 3 participants had elective abortions, 1 subject had a spontaneous abortion, and the outcome of 2 pregnancies remains unknown. Of the 9 live births, 3 were by cesarean section. Overall, no complications during pregnancy or congenital abnormalities at the time of birth were reported.

In HVTN 203 (91) there were 2 participants with miscarriages among the total of 80 female study participants who received ALVAC-HIV (vCP1452). These events were classified as unrelated to the study product by the investigators.

4.9.2.3 Summary of safety and tolerability data in African studies that have used ALVAC-HIV

To date, 3 studies have been completed in Africa with ALVAC-HIV: HIVNET 007, HPTN 027, and HVTN 097.

HIVNET 007 (92) was a randomized, double-blind, placebo-controlled clinical trial conducted in Kampala, Uganda. In this study, 40 HIV-seronegative Ugandan volunteers were randomly assigned to receive ALVAC-HIV (vCP205) (n = 20), control ALVAC containing the rabies virus glycoprotein G gene (n = 10), or saline placebo (n = 10). Adverse reactions to immunizations were similar to those in previous trials with these vaccines in HIV-seronegative volunteers in the United States. No severe (grade 3 or 4) adverse reactions attributable to receipt of the vaccine were observed.

HPTN 027 (93) was a phase 1 randomized, single center, double-blind, placebocontrolled trial that evaluated the safety and immunogenicity of ALVAC-HIV (vCP1521) in infants born to HIV-1–infected women in Uganda. 60 infants were enrolled with 48 in the active group and 12 in the placebo group. Forty-seven infants received all 4 vaccinations and completed follow-up (38 in the vaccine group and 9 in the placebo group). There were 3 deaths in the HPTN 027 study (2 in the vaccine group and 1 in the placebo group); all were reported as unrelated to the vaccine. The deaths included pneumonia-like illness, cor pulmonale secondary to congenital heart disease complicated by pneumonia, and gastroenteritis complicated with electrolyte imbalance. The rate of SAEs was similar between groups (56% in the vaccine group and 50% in the placebo group). In addition to the 3 deaths, 4 were discontinued from vaccination due to HIV infection (of whom 3 were HIV-positive at birth and 1 HIV-positive at 2 weeks; no other infant was found to be HIV-positive in the study); 1 was lost to follow-up; 6 (5 vaccine, 1 placebo) had AE requiring discontinuation (3 CD4 <25, anemia, gastroenteritis, increased liver enzymes). Thirteen infants in HPTN 027 experienced an AE that led to discontinuation of vaccinations: 10 participants in the vaccine group and 3 in the placebo group. There were no severe or life-threatening reactogenicity events. Mild reactogenicity events were common in both study arms, with only 1 moderate event (irritability) in the placebo group and 7 in the vaccine group (erythema, induration, pain, fever, and irritability).

In addition, the primary protocol for HVTN 097, which administered the RV144 vaccine regimen in a "low risk" South African population, is complete (Section 4.9.5).

4.9.2.4 Previous human experience with ALVAC-HIV used in combination with subunit protein boost adjuvanted with MF59

In addition to the ongoing HVTN 100 trial (Section 4.9.6), there has been meaningful previous human experience with the use of ALVAC-HIV vaccines in combination with recombinant gp120 proteins adjuvanted with MF59. In all, 440 participants had received this combination across 7 clinical trials before initiation of HVTN 100 (Table 4-7). No safety signal of concern was identified in these studies.

Study (Country)	ALVAC- HIV	Protein	Participants ^a
RV132 (88) (Thailand)	vCP1521	gp120 + MF59 clades B/E made in CHO cells	n = 45
AVEG 022A (94) (USA)	vCP205	gp120 + MF59 clade B made in CHO cells	n = 47
AVEG 029 (95) (USA)	vCP205	gp120 + MF59 clade B made in CHO cells	n = 22
AVEG 202/HIVNET 014 (96, 97) (USA)	vCP205	gp120 + MF59 clade B made in CHO cells	n = 145
AVEG 032 (98) (USA)	vCP205	gp120 +/- p24 + MF59 clade B gp120 made in CHO cells p24 made in S. cerevisiae	n = 56
AVEG 026 (99) (USA)	vCP300 ^b	gp120 + MF59 clade B made in CHO cells	n = 85
AVEG 012A 012B (100) (USA)	vCP125 ^c	gp120 + MF59 clade B made in CHO cells	n = 40
Total			N = 440

Table 4-7 Clinical studies performed with ALVAC-HIV and gp120+MF59

^a Number of participants who received both the ALVAC-HIV prime and the gp120/MF59 boost.

^b ALVAC-HIV (vCP300) is similar to vCP205 and contains additional sequences encoding Pol and Nef epitopes.

^c ALVAC-HIV (vCP125) contains the gene for gp160 from clade B.

